7. ADVERSE EVENT REPORTING

7.1 Adverse Events

7.1.1 *Adverse Event Reporting –*

All AEs from first dose (including premedication) until 30 days after the last administration of study treatment will be recorded on CRFs. Whenever possible, medical diagnoses should be captured instead of symptoms to prevent reporting more than one AE for a single event. A medical procedure is not considered an AE. Deaths are not be recorded as an event and are instead to be recorded as the outcome of an event. The condition that resulted in the death is to be recorded as the event.

Abnormal laboratory values that are clinically significant in the investigator's judgment will be recorded as AEs if there is not a related medical diagnosis. Severity (National Cancer Institute Common Terminology Criteria for Adverse Events [CTCAE] Version 50.3), relationship to study therapy, and any treatments given will be noted on the CRF. All related AEs must be followed until resolution or until the event is deemed stable or irreversible. All SAEs, regardless of relationship, should be followed until an outcome of the SAE can be documented. For patients discontinuing the study prematurely, all unrelated AEs are to be followed for 30 days after the last administration of study therapy, and all related AEs and SAEs are be followed as defined above. Cancer progression or cancer-related death will be considered a study endpoint and not an AE. Hospitalization for elective procedures or for protocol compliance is not considered an SAE. Relationship of an AE to the study drug is to be evaluated using the guidelines above.

7.1.2 *Serious Adverse Event Reporting*

All SAEs and pregnancies that occur between the first dose of study drug and 30 days after the last dose of study drug, whether or not considered related to the study drug, must be reported. In addition, SAEs occurring at any time that are attributable to study drug must be reported.

7.1.2.1 **The SAE report should include**

- a. date and time of onset
- b. description of event
- c. severity (CTCAE Version 4.0.3), duration
- d. outcome
- e. etiology
- f. relationship to study drug

- g. action taken
- h. other relevant details should be documented on these forms as available.
- i. SAEs related to other therapy or treatment must be reported as per local requirements.

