For the time period beginning at treatment allocation/randomization through 90 days following cessation of treatment, or 30 days following cessation of treatment if the subject initiates new anticancer therapy, whichever is earlier, any serious adverse event, or follow up to a serious adverse event, including death due to any cause other than progression of the cancer under study (reference Section 7.2.3.3 for additional details), [Note: this portion in blue text only applies to trials capturing Disease Progression as primary or secondary endpoint (PFS or ORR) – please delete if N/A]. whether or not related to the Merck product, must be reported within 24 hours to the Sponsor and within 2 working days to Merck Global Safety.

Additionally, any serious adverse event, considered by an investigator who is a qualified physician to be related to Merck product that is brought to the attention of the investigator at any time following consent through the end of the specified safety follow-up period specified in the paragraph above, or at any time outside of the time period specified in the previous paragraph also must be reported immediately to the Sponsor and to Merck Global Safety.

All subjects with serious adverse events must be followed up for outcome.

SAE reports and any other relevant safety information are to be forwarded to the Merck Global Safety [contact]

A copy of all 15 Day Reports and Annual Progress Reports is submitted as required by FDA, European Union (EU), Pharmaceutical and Medical Devices agency (PMDA) or other local regulators. Investigators will cross reference this submission

according to local regulations to the Merck Investigational Compound Number (IND, CSA, etc.) at the time of submission. Additionally, investigators will submit a copy of these reports to Merck & Co., Inc. (Attn: Worldwide Product Safety; [contact]) at the time of submission to FDA.

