11. STATISTICAL CONSIDERATIONS

The primary outcome of this study is overall response rate (CR+PR via RECIST 1.1). We will use a Simon's optimal 2-stage design with 80% power and 5% one-sided type-I error to compare the null hypothesis of ORR=5% vs. the alternative of ORR=20%. The first stage will enroll 10 patients, and if 1 or more responses are observed an additional 19 patients will be enrolled. If at least 4 responses are observed out of the 29 patients, the null hypothesis will be rejected

Safety Monitoring: We will monitor adverse events (AEs) throughout the study. If it appears that the risk of a serious AE is excessive, we will evaluate the treatment regimen and either modify the treatment plan or consider stopping the study. The risk of a serious AE (or DLT as defined above) is excessive if the risk is greater than 25%. Our stopping criterion corresponds to our determining that there is 75% or greater probability that the risk of a DLT exceeds 25%. Experience with single-agent anti-PD1 therapy suggests that the risk of a serious AE is between 15% and 20% but may be higher with the combination. We characterize this estimate with uncertainty using a beta distribution with parameters 2 and 8. This distribution has mean 0.2 and 90% probability that the risk is between 4% and 43%. The following table shows the stopping boundaries for safety monitoring.

Number of patients experiencing a DLT	4	5	6	7	8	9	10	11
Number of patients treated	4 - 6	7 - 9	10 - 13	14 - 17	18 - 20	21 - 24	25 - 27	28 - 29

Estimates of the operating characteristics for this stopping rule, as estimated from 5,000 simulations for each scenario, are as follows.

Risk of DLT	0.10	0.15	0.20	0.25	0.30	0.35	0.40	0.45	0.50
Chance of declaring the combination too toxic	1.2	4.8	14.2	31.2	51.7	71.5	86.9	94.9	98.3
Average sample size	28.8	28.1	26.6	24.0	20.8	17.2	13.7	11.1	9.1

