11.2 Interim Analysis

The first stage will enroll 10 patients, and if 1 or more responses are observed an additional 19 patients will be enrolled. After the first 6 patients are accrued, the regimen will be evaluated for toxicity. If 2 or more patients experience a DLT, the study will be halted for excess toxicity.

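### The toxicity rules count a DLT that is never defined, the six-patient halt has no minimum follow-up, and the printed safety figures do not describe the rules to be applied

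*Combined protocol and SAP*

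**What the plan says.** Under Safety Monitoring, Section 11 opens with "We will monitor adverse events (AEs) throughout the study". It commits the team, if serious AE risk looks excessive, to review the regimen and then modify the plan or consider stopping. The limit is worded as "The risk of a serious AE (or DLT as defined above) is excessive if the risk is greater than 25" per cent.

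The prior is justified by serious AEs: "Experience with single-agent anti-PD1 therapy suggests that the risk of a serious AE is between 15% and 20" per cent, expressed as a beta(2,8) distribution. The criterion is worded for DLTs: "there is 75% or greater probability that the risk of a DLT exceeds 25" per cent. The boundary table (4 events at 4-6 patients up to 11 at 28-29) and the operating characteristics (5,000 simulations per scenario) are also for DLTs.

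Section 11.2 adds a second rule: "After the first 6 patients are accrued, the regimen will be evaluated for toxicity", followed by "If 2 or more patients experience a DLT, the study will be halted for excess toxicity".

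Section 7 defines a serious AE. Section 7.1.2 requires that events up to "30 days after the last dose of study drug, whether or not considered related to the study drug, must be reported". Section 7.2.3.1 has another period, running "through 90 days following cessation of treatment, or 30 days following cessation of treatment if the subject initiates new anticancer therapy, whichever is earlier". Section 5, below the trial treatment table, allows first dose up to 14 days from registration.

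**The concern.** A stopping rule needs a counted event, a time by which each patient can be judged, and operating characteristics for the rule as it will be run. Each is incomplete here.

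Two teams could score the same six patients differently, because an unrelated hospitalisation counts if DLT means serious AE and may not otherwise. The result matters because the Section 11.2 halt is mandatory, whereas crossing the Section 11 boundary leads only to review. A look triggered by accrual may also be made on patients who have barely been exposed. Finally, anyone judging the safety plan from the printed table of operating characteristics would be judging a rule that differs from the one to be applied.

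**Working it through.** **Is a DLT defined anywhere?** The only mention of dose-limiting toxicity before Section 11 is background on a single-agent phase I trial (Section 2.5.2.2). Section 4.6 gives examples of toxicities for stopping one patient's treatment, in the investigator's opinion. Table 3 manages pembrolizumab patient by patient. Neither uses the term DLT, and neither gives an observation window for a trial-level count.

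**Reproducing the plan's figures.** Inputs from Section 11: beta(2,8) prior, 25% limit, 75% criterion, at most 29 patients. After x events in n patients the posterior is beta(2+x, 8+n−x). The smallest x with P(risk > 0.25) ≥ 0.75 is 3 at n=3-4, 4 at 5-8, 5 at 9-11, 6 at 12-15, 7 at 16-19, 8 at 20-22, 9 at 23-26 and 10 at 27-29.

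Stopping probabilities come from the exact recursion P_n(x) = P_{n−1}(x)(1−r) + P_{n−1}(x−1)r, removing mass at or above the limit after each patient. The response futility stop is left out; the printed mean of 28.8 patients at 10% risk indicates that the plan left it out too.

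| | 15% risk | 20% risk |
|---|---|---|
| Printed characteristics | 4.8%, mean n 28.1 | 14.2%, mean n 26.6 |
| 75% criterion, exact | 4.9%, 28.1 | 14.7%, 26.5 |
| Printed boundary row, exact | 2.1%, 28.7 | 8.0%, 27.8 |

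The simulation standard error at 14.2% is √(0.142 × 0.858 / 5000) = 0.5 points. The criterion is about one standard error from the printed value; the printed row is 14.2 − 8.0 = 6.2 points away, about twelve standard errors. So the printed characteristics belong to the 75% criterion and not to the printed row.

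Posterior probabilities at the printed entries run from 0.819 (9 of 24) to 0.923 (6 of 10), all above 0.75. For example, 4 of 8 gives beta(6,12), with P(risk > 0.25) = 0.765. That meets the criterion, but the row asks for 5.

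**Adding the 2-of-6 halt.** At 2 of 6 the posterior is beta(4,12), with P(risk > 0.25) = 0.461; the printed row needs 4 events at that point. Like for like at 20% risk, with the halt applied once at n=6:

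| | Without halt | With halt |
|---|---|---|
| Printed boundary row | 8.0%, mean n 27.8 | 35.8%, mean n 20.9 |
| 75% criterion | 14.7%, mean n 26.5 | 37.4%, mean n 20.7 |

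**Timing of the look.** With six fully observed patients, P(≥2) = 1 − (1−r)^6 − 6r(1−r)^5. If the sixth patient's event probability so far is h, it becomes P(≥2 of 5) + P(1 of 5) × h. With half the window observed and a constant hazard, h = 1 − (1−r)^0.5.

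- r = 0.30: full 1 − 0.118 − 0.303 = 0.580; half 0.472 + 0.360 × 0.163 = 0.531; none 0.472.
- r = 0.20: full 1 − 0.262 − 0.393 = 0.345; half 0.263 + 0.410 × 0.106 = 0.306; none 0.263.

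**The case against.** The best defence is that Section 11 equates the two terms in one sentence with one 25% limit, so DLT is another label for serious AE, which Section 7 defines. That is the more natural reading, and on it the prior fits. A reader might infer that the beta(2,8) prior describes a different event; that follows only if DLT is a separate event, which the wording does not favour. What stands is that the cross-reference points to nothing, and that serious AEs are collected whatever their cause.

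A reader might also infer that any admission for advancing cancer could force the halt. The documents do not support that. Section 7.1.1 treats progression and cancer-related death as endpoints and excludes elective and protocol-compliance hospitalisation. Section 7.2.3.3 excepts progression unless a causal link is suspected, and excludes convenience admissions. Other unrelated serious AEs would still count. The 30-day and 90-day periods both run from the end of treatment, so their difference matters little for an early look.

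On timing, looking after six are accrued need not mean at once, Section 10.1.1 starts toxicity evaluability at first treatment, and the Section 11 boundary keeps counting. The loss is modest, but nothing requires a wait.

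Two numerical inferences should be resisted. Setting the printed 14.2% against 35.8% mixes the boundary mismatch with the effect of the halt. Comparing halt probabilities at 15% and 20% risk only spans the plan's own serious AE range; it does not measure the missing definition.

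A strict early look at a posterior of 46% is a permissible conservative choice. The fault is that the two rules are not reconciled or evaluated together.

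**Conclusion.** The point holds, and the plan should be changed. That the counted event is undefined and that no minimum follow-up is stated are facts of the text. The definition gap has no numerical size, because the documents give no DLT rate separate from the serious AE range.

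The timing effect is 4 to 5 points for a half-observed sixth patient and 8 to 11 points if that patient is unobserved, at 20% and 30% risk. This assumes independent patients, a constant hazard and full observation of the first five. Fast accrual could leave more than one patient incomplete, but the documents give no accrual rate.

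The largest discrepancy is in the printed figures. At 20% risk, the top of the plan's single-agent range, the halt adds 28 points to the printed row (8.0% to 35.8%) and 23 to the criterion (14.7% to 37.4%), and cuts the mean sample size by about 6 to 7 patients.

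A reader might infer that patients are left unprotected. They are not: patient-level discontinuation rules, expedited reporting, cumulative monitoring and DSMB oversight remain. None of them says what the trial-level rules count.

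**What to change.** 1. Define one counted event covering both drugs, for example prespecified grade 3 or higher toxicities attributed to pembrolizumab or bavituximab; the choice is for the investigators. If serious AE is meant, say so, and state whether drug-unrelated events count and which reporting period applies. Use the same event in the 25% limit, prior, boundary, operating characteristics and Section 11.2, and confirm that beta(2,8) applies to it.
2. Hold the six-patient look until the sixth treated patient completes a fixed window from first dose, for example one 21-day cycle. Keep counting later events in the cumulative boundary, since Section 5.2.2 warns that immune events can be late.
3. Either replace the boundary row with the one the 75% criterion gives (listed in the working), or keep the printed row and restate the criterion to match it. State how the 2-of-6 halt combines with the boundary, and reissue the operating characteristics with both rules included.

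The cost is protocol wording, a short rerun and one accrual pause: 14 days from registration to first dose plus 21 days of window, so up to about 35 days.

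### The DLT stopping table does not follow from its own 75% criterion or give its stated operating characteristics, and the six-patient halting rule agrees with none of the three

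*Combined protocol and SAP*

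**What the plan says.** Section 11 (Statistical Considerations, Safety Monitoring) contains three linked statements.

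- **Criterion.** A DLT or serious-AE risk above 25% counts as too high, and the rule built on that limit reads: "Our stopping criterion corresponds to our determining that there is 75% or greater probability that the risk of a DLT exceeds 25"%. The prior is given: "We characterize this estimate with uncertainty using a beta distribution with parameters 2 and 8". Its mean is put at 0.2 and its 90% range at 4% to 43%.
- **Boundary table.** "The following table shows the stopping boundaries for safety monitoring". It runs from 4 DLTs at 4–6 patients treated to 11 DLTs at 28–29.
- **Operating characteristics.** "Estimates of the operating characteristics for this stopping rule, as estimated from 5,000 simulations for each scenario, are as follows". The chance of declaring the combination too toxic runs from 1.2% at a DLT risk of 0.10 to 98.3% at 0.50.

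When the risk appears excessive, the stated action is to evaluate the regimen and "either modify the treatment plan or consider stopping the study".

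Section 11.2 (Interim Analysis) adds a toxicity evaluation after the first 6 patients: "If 2 or more patients experience a DLT, the study will be halted for excess toxicity". It does not mention the criterion, table or operating characteristics in Section 11, and Section 11 does not mention it.

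**The concern.** A prior and a posterior cut-off determine the boundary at every sample size, and the boundary determines the operating characteristics. The three statements in Section 11 should therefore agree exactly, apart from simulation error. The six-patient rule looks far stricter than the table at the same point, and it is worded as a mandatory halt where Section 11 offers a choice of actions.

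If these disagree, investigators and the DSMB can reach opposite decisions from the same data. Anyone who judged the safety monitoring by the stated operating characteristics was judging a different rule.

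**Working it through.** **Inputs.** From Section 11: prior Beta(2,8), risk limit 0.25, cut-off 0.75, the printed boundary row, the stated operating characteristics and a maximum of 29 patients. From Section 11.2: halt if 2 or more of the first 6 have a DLT.

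**1. The prior.** Beta(2,8) has mean 2/10 = 0.20, and its 5th and 95th percentiles are 0.041 and 0.429. This is as stated.

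**2. Table against criterion.** After x DLTs in n patients the posterior is Beta(2+x, 8+n−x). The boundary is the smallest x with P(risk > 0.25) ≥ 0.75.

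| DLTs needed | Criterion: n | Printed table: n |
|---|---|---|
| 3 | 3–4 | – |
| 4 | 5–8 | 4–6 |
| 5 | 9–11 | 7–9 |
| 6 | 12–15 | 10–13 |
| 7 | 16–19 | 14–17 |
| 8 | 20–22 | 18–20 |
| 9 | 23–26 | 21–24 |
| 10 | 27–29 | 25–27 |
| 11 | – | 28–29 |

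The table needs one more DLT at n = 4, 7, 8, 10, 11, 14, 15, 18, 19, 21, 22, 25, 26, 28 and 29. It also has no entry at n = 3, where 3/3 gives 0.84. Results that meet the criterion but do not cross the table include 5/10 (0.83), 6/14 (0.80), 8/21 (0.80) and 10/28 (0.81).

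**3. Operating characteristics.** These were computed exactly, by carrying the distribution of the DLT count forward from patient 1 to 29 and checking the boundary after every patient. The last two columns add the Section 11.2 halt at n = 6. Entries are the chance of stopping (%).

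| Risk | Stated | Criterion | Table | Table + 11.2 | Criterion + 11.2 |
|---|---|---|---|---|---|
| 0.10 | 1.2 | 1.0 | 0.3 | 11.5 | 11.5 |
| 0.15 | 4.8 | 4.9 | 2.1 | 22.6 | 23.1 |
| 0.20 | 14.2 | 14.7 | 8.0 | 35.8 | 37.4 |
| 0.25 | 31.2 | 31.5 | 20.5 | 50.5 | 53.5 |
| 0.30 | 51.7 | 52.3 | 39.3 | 65.4 | 69.6 |
| 0.35 | 71.5 | 72.0 | 60.2 | 78.8 | 82.9 |
| 0.40 | 86.9 | 86.3 | 78.1 | 88.9 | 91.9 |
| 0.45 | 94.9 | 94.6 | 90.0 | 95.1 | 96.8 |
| 0.50 | 98.3 | 98.3 | 96.4 | 98.3 | 99.0 |

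Average sample size over the same risks:

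- Stated: 28.8, 28.1, 26.6, 24.0, 20.8, 17.2, 13.7, 11.1, 9.1
- Criterion: 28.8, 28.1, 26.5, 24.0, 20.6, 17.1, 13.8, 11.1, 9.0
- Table: 28.9, 28.7, 27.8, 26.1, 23.4, 20.1, 16.8, 13.8, 11.3
- Table + 11.2: 26.4, 23.8, 20.9, 17.9, 15.0, 12.3, 10.1, 8.4, 7.3

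The simulation standard error is √(p(1−p)/5000), at most about 0.7 points. The stated stopping chances lie within 1.3 standard errors of the criterion-based values at all nine risks. They lie 7 to 19 standard errors from the printed-table values. Looking less often would lower the table's stopping chances further, so the schedule of looks cannot explain the gap.

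A Beta(2,10) prior with the same cut-off reproduces the printed row at all 26 sample sizes. That may be how the row arose, but the protocol does not mention such a prior.

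**4. The six-patient rule.** The posterior P(risk > 0.25) is 0.46 at 2/6, 0.69 at 3/6 and 0.85 at 4/6, so table and criterion both first stop at 4. This look alone halts with probability 1 − (1−p)⁶ − 6p(1−p)⁵. That is 11.4% at p = 0.10, 34.5% at 0.20 and 46.6% at 0.25, against stated whole-study chances of 1.2%, 14.2% and 31.2%.

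Among trials that pass this look, the table still exceeds the criterion at 12 later sample sizes (n = 10 onward). Their later stopping chances at risks 0.25, 0.30, 0.35 and 0.40 are 7.3, 17.7, 33.5 and 52.2% with the table, and 13.0, 27.6, 46.3 and 65.2% with the criterion.

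**The case against.** The strongest reply concerns Section 11.2. A strict early look can be layered on a looser continuous rule, with the study stopping at whichever triggers first. Section 11.2 never claims to derive from the 75% criterion, and Section 11 ties its operating characteristics to its own stopping rule. On that reading, leaving the early look out is an omission and not an error, and the 0.46 posterior at 2/6 shows only that the two rules differ. That is a fair reading, but the protocol does not state it. It also leaves the protocol with no operating characteristics for the rules it will apply, and it does nothing for the mismatch between table and criterion.

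Layering does shrink the effect of that mismatch. With Section 11.2 in force, the printed and criterion-based boundaries differ by at most about 4 points in overall stopping chance (65.4% against 69.6% at a risk of 0.30). Crossing the table leads to a review and not an automatic halt, and a DSMB oversees the trial. Both points stand, and they limit the harm. They do not make the numbers right.

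The calculation also ignores the response-based stop at 10 patients. The stated values are reproduced on that same basis, so the comparison is like with like. As a check, assume a 5% response rate independent of toxicity, so that a fraction 0.95¹⁰ = 0.60 of the trials still open at 10 patients stop there. The table plus Section 11.2 then stops for toxicity in 81.6% of trials at a risk of 0.40, below the stated 86.9%. The excess at low risks remains: 35.0% against 14.2% at 0.20.

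Finally, the 15% to 20% range is the protocol's figure for serious AEs on single-agent anti-PD1 therapy, and the protocol adds that the combination may be higher. Section 11 treats serious AE and DLT as interchangeable and refers to a DLT definition that does not appear in the text supplied. That range is therefore only a reference point.

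**Conclusion.** The concern holds. The criterion and the stated operating characteristics agree with each other; the printed table agrees with neither. It is one DLT above the criterion at 15 of 26 sample sizes, and taken alone it stops up to 12.4 points less often than stated (39.3% against 51.7% at a risk of 0.30).

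The six-patient rule halts at half the DLT count that table and criterion require at that point. Once it is added to the printed table, the stopping chance exceeds the stated value at risks up to 0.40. At 0.45 and 0.50 the stopping chances agree, but the average sample size does not (8.4 and 7.3 against 11.1 and 9.1).

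These results assume that each patient's DLT status is known before the next is counted, that the boundary is checked after every patient, and that the response-based stop is left out. As written, the protocol gives conflicting safety thresholds and operating characteristics for a rule it will not apply, so this needs correcting.

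**What to change.** Reconcile four items in one amendment: the prior with its 75% criterion, the boundary table, the operating-characteristics table, and the six-patient rule in Section 11.2. The sponsor decides which toxicity rules stand. Then:

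1. Make the boundary row follow from the stated criterion, or restate the criterion so that it yields the row.
2. State whether the Section 11.2 rule applies in addition to the table or replaces it at 6 patients, and whether crossing a table boundary halts the study or starts a review.
3. Recompute the stopping chances and average sample sizes for the full set of toxicity rules, and say which rules they cover.
4. Point to the definition of the event being counted.

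The cost is changes to text and tables, with no extra patients or procedures. The restated figures may look less favourable: if the six-patient rule stays alongside either boundary, the chance of stopping at a 20% risk is 35.8% to 37.4%, not 14.2%.
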